2 nd dose reduction	400 mg PO QD	5 mg PO QOD
--------------------------------	--------------	-------------

If a patient on dose level +2 requires more than 2 dose reductions, then the patient will stop study therapy. If a patient has pneumonitis related to everolimus, then pazopanib dose level may be maintained and everolimus dose reduced or discontinued (see Table 6.2.3).

For patients on **dose level +2A** there will be 2 dose reductions allowed:

Dose Level	Pazopanib	Everolimus
Starting dose level +2A	800 mg PO QD	5 mg PO QD
1 st dose reduction	600 mg PO QD	5 mg PO QOD
2 nd dose reduction	400 mg PO QD	discontinue

If a patient on dose level +2A requires more than 2 dose reductions, then the patient will stop study therapy. If a patient has pneumonitis related to everolimus, then pazopanib dose level may be maintained and everolimus dose reduced or discontinued (see Table 6.2.3).

Phase I expansion cohort:

Individual patient dose reductions for toxicity will be determined by initial starting dose level in the Phase I expansion cohort which was dose level -1 as per results of the first phase of the study.

For patients on **dose level -1** there will be 1 dose reduction allowed:

Table 6 Dose Expansion cohort: Dose levels.

Dose Level	Pazopanib	Everolimus
Starting dose level -1	400 mg PO QD	5 mg PO QD
1 st dose reduction	200 mg PO QD	5 mg PO QOD

If a patient on dose level -1 requires more than one dose reduction, then the patient will stop study therapy. If, however, a patient is deriving benefit from one agent, as displayed by stable disease or better at restaging, and cannot tolerate the other, the patient may continue on monotherapy of the tolerated agent after discussion with the overall PI, [name]. If one agent is discontinued for toxicity, a patient may dose-increase to the standard monotherapy dose (see Table 7) of the other agent after discussion with the overall PI.

Table 7 Standard Monotherapy Dose Levels

Dose Level	Pazopanib	Everolimus
------------	-----------	------------

Dose level when other agent is discontinued due to toxicity	800 mg PO QD	10 mg PO QD
---	--------------	-------------

If a patient has pneumonitis related to everolimus, then pazopanib dose level may be maintained and everolimus dose reduced or discontinued (see Table 6.2.3).

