6.2.2 Management of hyperlipidemia & hyperglycemia

Adverse Drug Reaction	Severity	Everolimus Dose Adjustment and Management Recommendations
Metabolic events (e.g. hyperglycemia, dyslipidemia)	Grade 1	No dose adjustment required. Initiate appropriate medical therapy and monitor.
	Grade 2	No dose adjustment required. Manage with appropriate medical therapy and monitor.
	Grade 3	Temporary dose interruption. Re-initiate everolimus at lower dose. Manage with appropriate medical therapy and monitor.
	Grade 4	Discontinue everolimus and treat with appropriate medical therapy.

Treatment of hyperlipidemia should take into account the pre-treatment status and dietary habits of the patient. Grade 2 or higher hypercholesterolemia (>300 mg/dL or 7.75 mmol/L) or grade 2 hypertriglyceridemia or higher (>2.5 x upper normal limit) should be treated with a 3-hydroxy-3-methyl-glutaryl (HMG)-CoA reductase inhibitor (e.g. atorvastatin, pravastatin, fluvastatin) or appropriate triglyceride-lowering medication, in addition to diet.

Note: Concomitant therapy with fibrates and an HMG-CoA reductase inhibitor is associated with an increased risk of a rare but serious skeletal muscle toxicity manifested by rhabdomyolysis, markedly elevated creatine phosphokinase (CPK) levels and myoglobinuria, acute renal failure and sometimes death. The risk versus benefit of using this therapy should be determined for individual patients based on their risk of cardiovascular complications of hyperlipidemia.

Dyslipidemia (including hypercholesterolemia and hypertriglyceridemia) has been reported in patients taking everolimus. Monitoring of blood cholesterol and triglycerides prior to the start of everolimus therapy and periodically thereafter as well as management with appropriate medical therapy is recommended.

Hyperglycemia has been reported in patients taking everolimus. Monitoring of fasting serum glucose is recommended prior to the start of everolimus and periodically thereafter. More frequent monitoring is recommended when everolimus is co-administered with other drugs that may induce hyperglycemia. Optimal glycemic control should be achieved before starting a patient on everolimus.

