6.3 Dose Modifications/Delays

6.3.1 General dose modification/Delays

Dose modifications for toxicities not otherwise covered in section 6.2 are listed in the table below. Patients who do not recover to grade 2 or less toxicity within 28 days will be removed from protocol therapy except where noted (ie. pneumonitis). In addition, patients may hold study intervention (pazopanib and everolimus) for greater than 28 days if the patient's physician and the overall principal investigator, [name], agree that the patient is deriving clinical benefit from the study drugs. Dose modifications for specific toxicities are covered in sections 6.2 and 6.3.

All toxicities, both during the DLT period and after it has been completed, will follow the guidelines laid out here in sections 6.2 and 6.3.

For definition of a Dose Limiting Toxicity, refer back to section 5.4.

Non-hematological toxicity

Toxicity	Actions
Non-Infectious Pneumonitis	Please refer to section 6.2.3
Reactivation of HBV or HCV flare	Please refer to section 6.2.4
Non-hematological toxicity Grade 2 (except pneumonitis – refer to section 6.2.3) (except hypertension, proteinuria, venous or arterial thrombosis, QTc prolongation- refer to section 6.3.2) (except hepatotoxicity – refer to section 6.3.3) (except elevated amylase and lipase- refer to section 6.3.5)	If the toxicity is tolerable to the patient, maintain the same dose. If the toxicity is “intolerable” to patient, interrupt pazopanib and everolimus until recovery to grade ≤ 1 . Then reintroduce pazopanib and everolimus at same dose. If event returns to “intolerable” grade 2, then interrupt pazopanib and everolimus until recovery to grade ≤ 1 . Then reintroduce pazopanib and everolimus at one dose level lower. If event is recurrent “intolerable” grade 2 despite two dose reductions, discontinue pazopanib and everolimus.
Grade 3 or 4 (except hyperlipidemia ¹) (except pneumonitis – refer to section 6.2.3) (except hypertension, proteinuria, venous or arterial thrombosis, QTc prolongation- refer to section 6.3.2) (except hepatotoxicity – refer to section 6.3.3)	Interrupt pazopanib and everolimus until recovery to grade ≤ 1 . Then reintroduce pazopanib and everolimus at one dose level lower. No more than 2 dose reductions allowed.
Stomatitis / oral mucositis / mouth ulcers	See section 6.2.3 Management of stomatitis / oral mucositis / mouth ulcers

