Recurrence of grade 3 toxicity after dose reduction	Reduce dose to the next lower dose level, if available. The lowest possible dose level of everolimus is 5 mg every other day (2.5 mg daily). Below this level, everolimus must be discontinued.
	Interrupt everolimus administration until resolution to \leq grade 1 or baseline

Intolerable grade 2 mucositis, or grade 3 AE, except hyperglycemia or hypertriglyceridemia or hypercholesterolemia (see Section 6.2.2.)	
grade / value.
 
If resolution occurs within \leq 7 days, everolimus should be re-started at the dose level prior to interruption.
 
If resolution takes $>$ 7 days, or if event recurs within 28 days, hold everolimus until recovery to \leq grade 1 or baseline grade / value and reintroduce everolimus at one dose level lower, if available.
 
Patients will be withdrawn from the study if they fail to recover to \leq grade 1 or baseline grade / value within 28 days.

Any other grade 4	
Hold everolimus until recovery to grade \leq 1 or baseline value
 
Reintroduce everolimus at one dose level lower, if available.

Grade 3 or 4 clinical liver failure (asterixis or encephalopathy/coma)	
Discontinue everolimus and Pazopanib

Recurrence of intolerable grade 2 mucositis or grade 3 event after dose reduction	
Reduce dose to the next lower dose level, if available. The lowest possible dose level of everolimus is 2.5 mg daily. Below this level, everolimus must be discontinued. If toxicity recurs at Grade 3, consider discontinuation.

Recurrence of grade 4 after dose reduction	
Discontinue everolimus and Pazopanib

Any non-hematologic toxicity requiring everolimus interruption for $>$ 28 days	
Discontinue everolimus and Pazopanib

¹Grade 3 hyperlipidemia (hypercholesterolemia and/or hypertriglyceridemia) should be managed using medical therapies without dose reduction (see Section 6.2.2).

Hematological toxicity

Grade 2 Thrombocytopenia (platelets $<75 - 50 \times 10^9/L$)	
Interrupt pazopanib and everolimus until recovery to grade \leq 1 ($\geq 75 \times 10^9/L$). Then reintroduce pazopanib and everolimus at initial dose. If thrombocytopenia again returns to grade 2, interrupt pazopanib and everolimus until recovery to grade \leq 1. Then reintroduce everolimus at one dose level lower. No more than two dose reductions are allowed.

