Grade 3 or 4 Thrombocytopenia (platelets $<50 \times 10^9/L$)	
Interrupt pazopanib and everolimus until recovery to grade \leq 1 ($\geq 75 \times 10^9/L$). Then resume pazopanib and everolimus at one dose level lower. If grade 3 or 4 thrombocytopenia recurs, discontinue pazopanib and everolimus.

Grade 1 & 2 Neutropenia (neutrophils $\geq 1 \times 10^9/L$)	
Grade 3 Neutropenia (neutrophils $<1, \geq 0.5 \times 10^9/L$)	
No modification of dose.

	
Interrupt everolimus and Pazopanib until resolution to grade ≤ 1 or baseline value
 
If AE resolution occurs ≤ 7 days, reintroduce everolimus and pazopanib at the same dose level.
 
If AE resolution occurs > 7 days (within 28 days), reintroduce everolimus and pazopanib at one dose level lower, if available. Discontinue patient from study therapy if recurrent grade 3 or greater neutropenia after two dose reductions.

Grade 4 Neutropenia (neutrophils $< 0.5 \times 10^9/L$)
	
Interrupt pazopanib and everolimus until recovery to grade ≤ 1 (neutrophils $\geq 1.5 \times 10^9/L$). Then resume pazopanib and everolimus at one lower dose level. If grade 3 or grade 4 neutropenia occurs despite two dose reductions, discontinue pazopanib and everolimus.

Grade 3 febrile neutropenia (not life-threatening)
	
Hold further pazopanib and everolimus until the ANC $\geq 1,500/\text{mm}^3$ and fever has resolved and antibiotics are discontinued. Then resume pazopanib and everolimus at one dose level lower. If febrile neutropenia recurs, discontinue pazopanib and everolimus.

Grade 4 febrile neutropenia (life-threatening)
	
Discontinue pazopanib and everolimus.

Any hematological or non-hematological toxicity requiring interruption for ≥ 4 weeks
	
Discontinue pazopanib and everolimus

6.3.2 Management of hypertension, proteinuria, hemorrhage/bleeding, venous and arterial thrombosis, QTc prolongation

AE Terms & Descriptions	Dose Modification Algorithms

Hypertension
	

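### Table 6 gives expansion patients one dose reduction, four toxicity rows in 6.3 discontinue only after two, and grade 3 dyslipidemia has two conflicting instructions

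*Combined protocol and SAP*

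**What the plan says.** **Number of reductions.** Section 5.1 sets the expansion dose at pazopanib 400 mg and everolimus 5 mg daily, which is dose level -1. The expansion part of Section 6 says that "Individual patient dose reductions for toxicity will be determined by initial starting dose level in the Phase I expansion cohort". For level -1, "there will be 1 dose reduction allowed", and Table 6 lists one lower step (pazopanib 200 mg daily with everolimus 5 mg every other day). Then: "If a patient on dose level -1 requires more than one dose reduction, then the patient will stop study therapy". A patient with stable disease or better who cannot tolerate one agent may continue on the other alone, after discussion with the overall principal investigator.

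**Toxicity tables.** Sections 6.2 and 6.3.1 both state that all toxicities, during and after the DLT period, follow 6.2 and 6.3. Neither makes an exception for a cohort or a starting level. In 6.3.1, the grade 3-4 non-hematological row ends "No more than 2 dose reductions allowed", and the grade 3 neutropenia row ends "Discontinue patient from study therapy if recurrent grade 3 or greater neutropenia after two dose reductions". The proteinuria steps in 6.3.2 reduce one level at the first event, repeat this at the first recurrence, and discontinue on recurrence after two reductions.

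**Grade 3 dyslipidemia.** The metabolic-events table in 6.2.2 says "Temporary dose interruption. Re-initiate everolimus at lower dose". Footnote 1 of 6.3.1 says that grade 3 "hyperlipidemia (hypercholesterolemia and/or hypertriglyceridemia) should be managed using medical therapies without dose reduction", and refers the reader back to 6.2.2.

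**The concern.** For some toxicities the protocol gives an expansion patient two instructions that cannot both be followed. At the same event, one page stops study therapy and another reduces again, to a level that does not exist for this cohort. Two centres enrol, and nothing in the text makes them choose the same page.

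The first thing at stake is safety: whether a patient with recurrent toxicity stays on the combination. The second is interpretation of the secondary endpoints. Rates of discontinuation for toxicity, and exposure, would depend partly on which table a site used. Section 14.4 censors progression-free survival and duration of response at the last disease evaluation, so a difference in when patients stop could carry over to those estimates. A responder taken off therapy early might also miss the confirmatory scan that Section 10 requires at least 4 weeks later.

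**Working it through.** No formula applies. The check counts, for a patient starting at level -1, the reductions each text allows before stopping, and compares that with the dose levels defined.

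**Step 1. Levels available.** Table 6 has the starting level and one lower level, so one reduction can be carried out.

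**Step 2. Reductions each text contemplates.**

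| Text | Reductions before stopping | Fit with Table 6 |
|---|---|---|
| Section 6, Table 6 | 1 | reference |
| Proteinuria (6.3.2) | 2; the second is ordered at first recurrence | conflicts |
| Intolerable grade 2 non-hematological (6.3.1) | discontinue only after 2 | conflicts |
| Grade 3 neutropenia (6.3.1) | discontinue only after 2; lower level if available | conflicts on when to discontinue |
| Grade 4 neutropenia (6.3.1) | discontinue only after 2 | conflicts |
| Grade 3-4 non-hematological (6.3.1) | at most 2 | can be read as compatible |
| Grade 2 thrombocytopenia (6.3.1) | at most 2 | can be read as compatible |
| Recurrent grade 3-4 thrombocytopenia, febrile neutropenia, ALT above 8 x ULN, grade 4 non-hematological toxicity, grade 2 or higher bleeding | 1 at most | compatible |
| Arterial thrombosis, QTc of 500 msec or more, grade 4 venous thrombosis and/or PE, grade 4 febrile neutropenia | 0 | compatible |

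**Step 3. One patient traced through the clearest row.** A patient at level -1 reaches 24-hour urine protein of 3 g or more, is interrupted, and restarts at the only lower level. The proteinuria then recurs. Under Section 6 the patient now needs a second reduction and stops study therapy. Under 6.3.2 the patient is interrupted and restarted one level lower again. Two reductions are contemplated and one level is defined, so the second has no stated dose. This row carries no wording that limits it to levels that exist.

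**Step 4. The other three rows.** Each makes discontinuation depend on two earlier reductions. With one lower level, an expansion patient cannot have had two, so the condition as written is never met. Table 6 would stop the same patient when the second reduction was needed.

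**Step 5. Is there a precedence rule?** The opening of 6.3.1 says its table is for toxicities that 6.2 does not cover. That ranks 6.2 against 6.3.1. It does not rank Table 6 against 6.3.1 or 6.3.2, and no other sentence does.

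**Step 6. Grade 3 dyslipidemia.** 6.2.2 interrupts and restarts everolimus at a lower dose. Footnote 1 says no dose reduction and cites 6.2.2 as its source. The cross-reference leads to the opposite instruction. This conflict does not depend on the number of reductions.

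**Step 7. Lowest everolimus level.** One 6.3.1 row says "The lowest possible dose level of everolimus is 2.5 mg daily". Another row in the same table gives 5 mg every other day with 2.5 mg daily in brackets, so the protocol treats the two as equivalent, and the first matches Table 6. Section 7.1.2 lists a 2.5 mg tablet, so one consistent expression would be clearer, but no dose conflict is shown.

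**The case against.** The best defence is that Section 6.3 was written for every cohort. Levels +1, +2 and +2A do allow two reductions, so a general limit of two makes sense there, and the expansion text sets the count by starting level. The specific rule then operates inside the general ceiling. This stands for the two rows worded as a maximum: one reduction followed by stopping satisfies both texts. It does not rescue proteinuria, which orders the second reduction, or the three rows that discontinue only after two. The words about availability in the grade 3 neutropenia row soften the reduction, not the discontinuation condition.

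A second defence is that a site has no second dose to give, that monotherapy is an outlet, and that monthly calls link the centres. These make divergence less likely. But monotherapy is conditional on benefit, on intolerance of one agent and on discussion with the overall principal investigator, and the calls are not a written rule.

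For dyslipidemia, the opening of 6.3.1 can be read as giving 6.2.2 priority. That helps, but footnote 1 still contradicts the section it cites.

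A reader might infer that the toxicity tables as a whole act only after two reductions. They do not: the last two rows of the comparison list nine situations that stop after one reduction at most. A reader might also take the two expressions of the lowest everolimus level as a dose conflict. The document's own equation of them does not support that.

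**Conclusion.** The contradiction holds as a matter of text. For expansion patients, four rows (proteinuria, intolerable grade 2 non-hematological toxicity, grade 3 neutropenia, grade 4 neutropenia) cannot be squared with Table 6, and the two grade 3 dyslipidemia instructions cannot both be followed. The two maximum-of-two rows need aligning only for clarity. This is an error as written, because it concerns rules for managing patients. It rests on the documents' own statements that both Table 6 and Sections 6.2-6.3 apply to these patients.

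No patient count can be attached. A reader might take the Phase I report that 2 of 6 patients at this dose came off for toxicity after 2 cycles and apply it to the 26 to 29 patients of Section 14.1 (26 x 2/6 = 8.7; 29 x 2/6 = 9.7). The documents do not support that step. They do not say that either patient had a dose reduction, needed a second one, or had one of the toxicities above. The exact 95% interval for 2 of 6, about 4% to 78%, is also too wide to be useful.

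Nor do the documents support a claim that the primary analysis is invalid. Section 14.1 counts eligible patients who start therapy, so the response denominator, the stated type I error of 0.099 and the stated power of 0.904 do not depend on this point. An effect on exposure, progression-free survival, duration of response or confirmation of an individual response is possible, but its size is unknown.

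**What to change.** - Reconcile the proteinuria, intolerable grade 2 non-hematological, grade 3 neutropenia and grade 4 neutropenia rows with Table 6, so that one number of reductions and one set of levels applies to the expansion cohort.
- Align the wording of the grade 3-4 non-hematological and grade 2 thrombocytopenia limits with the same count.
- Reconcile the grade 3 metabolic row of 6.2.2 with footnote 1 of 6.3.1.
- State which text prevails when Table 6 and a row of 6.2 or 6.3 both apply.
- As a tidy-up, write the lowest everolimus level one way throughout.

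Which clinical rule to adopt is for the sponsor; this point takes no position on it. The cost is a protocol wording amendment with the usual IRB review. Sample size, stopping boundary and analysis stay as they are.

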6.1 Anticipated Toxicities

6.1.1 Everolimus

Adverse events most frequently observed with everolimus are rash, stomatitis/oral mucositis, fatigue, headache, anorexia, nausea, vomiting, diarrhea. Infections have not been notably frequent or severe. Non-infectious pneumonitis has also been observed. The majority of these AEs have been of mild to moderate severity (CTC grade 1-2). Overall, the most frequently observed laboratory abnormalities include reduced blood counts, hyperlipidemia mostly reported as hypercholesterolemia and/or hypertriglyceridemia.

Hyperlipidemia was reported as a serious adverse reaction. It is a recognized side-effect of rapamycins. Use of lipid-lowering drugs should be associated with dietary recommendations. Monitoring of blood lipid levels requires patients to be fasting so that this aspect must be verified when interpreting results.

Hyperglycemia was reported as a serious adverse reaction. Similarly, the fasting state of patients should be verified when interpreting results.

Pneumonitis is a recognized adverse effect of rapamycins (sirolimus, temsirolimus, and everolimus). Numerous case reports in the literature suggest that rapamycin-associated pneumonitis is relatively unaggressive, limited in extent, and reversible upon drug discontinuation. The term 'pneumonitis' is used here to describe non-infectious, nonmalignant infiltration in the lungs which is evident radiologically. More precise diagnosis should follow histocytological examination following lung biopsy, generally during bronchoscopy which may or may not be symptomatic. Advice on the management of pneumonitis has been provided in Table 6.2.3. In oncology studies with everolimus, severe pneumonitis suspected as drug-related has been reported as a serious adverse event on 13 occasions and additionally in the following associated preferred terms including acute respiratory distress syndrome (n=2), alveolitis (n=1) and allergic alveolitis (n=1), interstitial lung disease (n=10), lung infiltration (n=23), cryptogenic organizing pneumonia, lung consolidation, pulmonary alveolar haemorrhage, pulmonary toxicity and pulmonary fibrosis (n=1, each). One fatal case of drug-related pneumonitis was reported for a patient with metastatic infiltrating ductal carcinoma of the breast treated with 10 mg/day, which developed approximately two months after starting everolimus. Cytology for both the pleural and pericardial fluids were positive for malignancy. The death was considered possibly related to the underlying late stage tumor and study drug. Additionally, one patient treated

with 10 mg/day died due to severe acute respiratory distress syndrome and septic shock. Thoracic CT scan demonstrated condensation in the majority of the left lower lobe and frosted glass appearance in the left upper lobe, lingula, and right lung. Along with the cases of non-infectious pneumonitis, serious opportunistic infections have also been reported in cancer patients treated with everolimus: mycobactrium, aspergillus, and fatal candidal sepsis, and fatal pneumocystis carni in particular. Because everolimus, as other rapamycins, inhibits proliferation of activated lymphocytes and reduces neutrophil counts, treatment with everolimus must be considered as predisposing patients to the risk of infection. This risk will be higher in patients severely immunocompromised because of their underlying disease and/or co-medications. Outcome may be fatal in case of serious infections.

A reduction in blood cell counts is frequent when everolimus therapy is initiated. Without clinical significance and infrequently, anemia and thrombocytopenia have been reported. In heavily pretreated patients with aggressive lymphoma, the incidence of grade 3 anemia, neutropenia, and thrombocytopenia was reported to be 11%, 16%, and 30%, respectively. Serious, suspected drug-related hemorrhages have been exceptional. Nevertheless, everolimus should be considered as predisposing patients to hemorrhage, potentially fatal, should they develop severe drug-related thrombocytopenia.

Discrete, reversible changes in liver enzymes have been found to occur in numerous patients during treatment with everolimus in oncology clinical studies, and in a study in rheumatoid arthritis. In oncology studies, these changes may be evident only in patients without severe underlying morbidity. The increase in transaminase's (AST and ALT) generally appears after 4 weeks of treatment. In all but a few cases it does not exceed Grade 1 ($\leq 2.5 \times$ institution ULN).

Similarly, mild increases in alkaline phosphatases can coexist. Spontaneous corrections or intermittent correction with continued treatment can occur. Serum bilirubin is not increased. In studies of patients with advanced cancers, clinically relevant changes in liver enzymes have been invariably associated with the presence of liver metastases and/or progression of the underlying cancer.

Renal failure has been reported in five suspected cases to date. One patient with no alternative explanation made a complete recovery following study drug adjustment and no treatment/therapy for the event. The rest of the patients had concurrent morbidities, which might have contributed to the reported events.

Hypophosphatemia, hypomagnesemia, hyponatremia and hypocalcemia have been reported as serious adverse reactions. Electrolytes should be monitored in patients treated with everolimus.

